### **I. Hypotheses and Specific Aims:**

Every year, alcohol use disorder (AUD) generates millions of emergency department (ED) visits and hospital admissions, costing the U.S. health sector over \$90 billion. These hospital admissions are critical opportunities to start patients on addiction pharmacotherapy, but factors like medication non-adherence and post-discharge relapse contribute to frequent re-admissions. Two single-dose interventions are well suited to facilitate treatment retention and prevent re-admissions due to their prolonged, adherence-independent effects: extended-release (XR) naltrexone injection and intravenous (IV) ketamine infusion. These have not been thoroughly investigated in the hospital setting among high-utilizer, safety-net populations. Therefore, we aim to:

- 1. Test the feasibility of randomizing hospitalized patients (n=45-60, age 18-65) with multiple AUD-related admissions to treatment with either extended-release (XR) naltrexone, intravenous (IV) ketamine, or no single-dose medication, all with enhanced linkage to care.** Feasibility outcomes such as recruitment rate, patient acceptability, post-discharge follow-up rate, and adverse events will help to identify key lessons for a future comparative effectiveness study.
- 2. Estimate the 30-day re-admission rate for patients randomized to treatment with XR naltrexone, with IV ketamine, or no single-dose medication, all with enhanced linkage to care.** We hypothesize that the re-admission rate will be lower for each of the two single-dose medication groups than for the “linkage-alone” group.

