### III. Preliminary Studies/Progress Report:

There have been no preliminary studies. However, an initial Tableau query showed that at Denver Health, patients admitted to the hospital with an alcohol related diagnosis had a 30-day readmission rate of between about 10 and 40 percent (see Figure 1). This is notably an underestimation, given that patients may have had readmissions at hospitals outside of Denver Health, which would not have been captured in those data.

There is also low outpatient treatment engagement following discharge for these patients. I reviewed a cohort of 17 patients that I cared for in August and September 2019, all of whom I referred to outpatient addiction clinic for treatment of alcohol use disorder. Only 2 presented within the following month. Among the 9 who were prescribed oral naltrexone, only 1 presented.

[figure not shown]

Figure 1 DH hospital re-admissions. Obtained via Tableau with assistance from [name]. Alcohol admissions based on All-Patients-Refined-Diagnosis-Related-Groups (APR-DRG) 775 and 280.

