### C. Study Design and Research Methods

We propose an open-label, pilot feasibility trial (n=45-60), randomizing hospitalized patients to receive XR naltrexone, IV ketamine, or neither prior to hospital discharge, along with enhanced linkage to care. The primary clinical

outcome compared across each of the groups will be 30-day re-admission rates ascertained by chart review (Table 1).

To reduce variability, all participants will undergo a standard addiction consultation that includes behavioral components such as supportive therapy and motivational interviewing. They will also receive enhanced linkage to care (hereon “linkage”) which includes being met by a staff member while in the hospital to begin the clinic intake process and assign a follow-up appointment date. Linkage will also include a contingency management (monetary incentive to follow-up) in their post-hospital transition and receive standard case management and counseling at Substance Use Disorder Services (SUDS) clinic.

ACS team members will identify patients meeting inclusion criteria (Table 2), and – after conducting their usual consultation – approach them about the study. Approximately 900 patients met similar inclusion criteria in 2019 (Query by [name]). After screening for exclusion criteria, informed consent will occur, and initial baseline data will be obtained by “Treatment on Demand” (TOD), a grant-funded team of counselors who are already linking hospitalized patients to addiction care. Consented patients will then be randomized, and the ACS will work with the primary team to order and administer the assigned intervention close to discharge. Meanwhile, a TOD counselor will work to establish a follow-up date within seven days post-discharge. Additional data will be collected immediately after the intervention (for those in one of the two medication groups), at SUDS follow up, and 30-days post-discharge by chart review.

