30-day chart review [data collection point #4]	Research staff	Should check encounters tab as well as “care everywhere” for Denver Metro region.	
 
Admissions (up to 5) within 30 days of discharge date (date, location, up to top 3 main diagnoses based on documentation available).
 
ED visits (up to 5) within 30 days of discharge date (date, location, up to top 3 main diagnoses based on documentation available).
 
AST, ALT obtained at SUDS f/u (if available)
 
Urine EtG obtained at SUDS f/u (if available)
 

Screening: The addiction consult team will attempt to screen patients meeting the inclusion criteria during inpatient admission. We anticipate 10 patients will meet inclusion criteria weekly. They will be assessed for clear exclusion criteria documented in the chart, and if none are noted the patient will be asked if they would like to join the study and complete the screening. If still no exclusion criteria are met and the patient expresses interest, they will be engaged in informed consent. The primary team will be notified by the addiction medicine team. Each combined process of screening and consent is anticipated to require 15 minutes at the end of a typical consultation. The screening window is anticipated to last 5 months.

Randomization: Patients will undergo a simple randomization algorithm to one of three arms.

Intervention:

- **Arm 1:** Receive a single dose of XR naltrexone (380mg) prior to discharge.
- **Arm 2:** Receive a single infusion of IV ketamine (0.5 mg/kg over 40 minutes) prior to discharge.
- **Arm 3:** No single-dose medication
- *All groups will receive enhanced linkage to care that includes contingency management, initiation of biopsychosocial intake, and appointment scheduling. This aspect alone surpasses the current standard of care.*

Contingency Management: Patients will receive a debit card prior to discharge from the hospital. We will utilize a pre-existing system - ClinCard by Greenphire. Participants will receive \$10 upon completion of baseline data, and \$20 upon completion of follow-up data (at SUDS clinic).

Follow up: Patients will be assigned a follow-up within 7 days of discharge at the outpatient addiction clinic (Denver Health SUDS clinic in pavilion K).

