#### **F. Data Analysis Plan:**

Participants’ demographic and baseline clinical data will be tabulated, and differences between groups will be assessed using a Fisher’s Exact Test for categorical variables and a two-sample t-test for continuous variables. These tests

will help evaluate the effectiveness of randomization. Feasibility outcomes (Aim 1) such as adverse events and acceptability (Likert scale) will be compared for each group using a Fisher's Exact Test and Wilcoxon-Mann-Whitney Test, respectively. Overall recruitment rate and follow-up rate will be tallied at the conclusion of data collection.

For Aim 2, all-cause hospital re-admission within 30-days of discharge will be recorded as a binary outcome. Rates of the two medication intervention groups (XR naltrexone or IV ketamine) will be compared against the group that received enhanced linkage to care alone.

This pilot study may not be sufficiently powered for robust hypothesis testing. By one crude estimate, we could have approximately 80% power to detect a difference between a medication group and the linkage-alone group with about 60 participants assuming a re-admission rate is 25% vs 15%. A larger effect size would increase our power and/or reduce the number of participants required. Regardless, this will provide parameter estimates that can inform a future sample size calculation in a larger effectiveness trial.

For further descriptive purposes, a secondary utilization outcome is risk of 30-day all-cause ED visits. This will be evaluated in a similar manner as hospital re-admissions. Additionally, we are interested in the within-subject difference in readiness-to-change. For those who follow-up, a mean of pre/post differences will be calculated, and a paired t-test will be used to determine if the null hypothesis ( $H_0$ : difference = 0) can be rejected. Drinking behavior will be measured using the Timeline Follow Back method. Binge drinking will be defined as 5+ drinks for men, 4+ for women, and the proportion of binge drinking days since discharge will be calculated for each group. Proportions of positive urine ethyl glucuronide (EtG) will also be tabulated for each group.

Data will be analyzed in SAS.

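### The stated power of about 80% for 25% vs 15% re-admission with about 60 participants is wrong; at 20 per arm it is about 12%

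*Combined protocol and SAP*

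**What the plan says.** Section IV.F (Data Analysis Plan) first warns: "This pilot study may not be sufficiently powered for robust hypothesis testing". It then gives, as a crude estimate, the protocol's only power figure: "we could have approximately 80% power to detect a difference between a medication group and the linkage-alone group with about 60 participants". The rates behind that figure are 25% for linkage-alone and 15% for the drug. It adds that a larger effect would raise power or lower the number needed, and that the data will in any case inform a later sample size calculation.

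The sample size is a total over three arms. Section IV.C describes an "open-label, pilot feasibility trial (n=45-60), randomizing hospitalized patients to receive XR naltrexone, IV ketamine, or neither prior to hospital discharge", and its randomization paragraph says "Patients will undergo a simple randomization algorithm to one of three arms". Re-admission within 30 days is the primary clinical outcome in Table 1, and Aim 2 in section I carries a directional hypothesis: "We hypothesize that the re-admission rate will be lower for each of the two single-dose medication groups".

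The documents give no alpha, sidedness, allocation ratio, power formula or named test for re-admission. Fisher's exact test is named only for categorical baseline variables and adverse events.

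**The concern.** A 10-point difference between two proportions near 20% is small relative to the sampling error of groups of about 20, so 80% power is implausible on sight. The 60 participants are also spread over three arms, and only about 40 of them enter any one comparison.

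Two things are at stake. A reader who accepts 80% could take a non-significant re-admission result as evidence against a drug, when the trial had little chance of showing the assumed effect. The figure could also be carried into planning of the larger trial as a benchmark that about 60 patients suffice for a 10-point difference.

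**Working it through.** **Inputs**

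- Rates: linkage-alone p1 = 0.25, drug p2 = 0.15 (IV.F).
- Total sample size: 45 to 60 over three arms (I and IV.C).
- Comparison: each drug arm against linkage-alone (IV.F).
- Assumed, because not stated: 1:1:1 allocation (20 per arm at 60, 15 at 45), two-sided 5%, and no missing outcomes (re-admission comes from chart review).

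**Power at 20 per arm, normal approximation**

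The mean rate is 0.20.

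- Standard error under no difference: √(2 × 0.20 × 0.80 / 20) = √0.016 = 0.1265.
- Standard error under the alternative: √((0.25 × 0.75 + 0.15 × 0.85) / 20) = √((0.1875 + 0.1275) / 20) = 0.1255.
- Power = Φ((0.10 − 1.96 × 0.1265) / 0.1255) = Φ(−1.18) = 0.119.

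Exact enumeration over all outcomes gives 0.121 for the chi-square test and 0.067 for Fisher's test. At 15 per arm these are 0.103 and 0.043. The stated 80% is not reproduced.

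**Sample size for 80% power**

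n per arm = (1.96 × √(2 × 0.20 × 0.80) + 0.842 × √(0.1875 + 0.1275))² / 0.10² = (1.109 + 0.472)² / 0.01 ≈ 250.

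Exact chi-square power at 250 per arm is 0.803. One comparison therefore needs about 500 patients, and three equal arms about 750. At one-sided 5% the requirement is 197 per arm.

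**Can another reading give 80%?** Chi-square power by exact enumeration, 25% vs 15%:

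| Reading | Alpha | Power |
|---|---|---|
| 20 vs 20 | two-sided 5% | 0.121 |
| Average over arm sizes from simple randomization of 60 to three equal-probability arms | two-sided 5% | 0.121 |
| 30 vs 30 (all 60 in the comparison) | two-sided 5% | 0.157 |
| 20 vs 40 (drug arms pooled) | two-sided 5% | 0.158 |
| Best split of up to 60, at least 10 per group (25 linkage, 35 drug) | two-sided 5% | 0.206 |
| 60 vs 60 (60 misread as per arm) | two-sided 5% | 0.278 |
| 20 vs 20 | one-sided 5% | 0.197 |
| 20 vs 20 | one-sided 10% | 0.307 |
| 20 vs 20 | one-sided 20% | 0.485 |
| 60 vs 60 | one-sided 20% | 0.715 |

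By the normal approximation, 80% power at 20 per arm would need a one-sided alpha of about 0.52.

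**What the trial can estimate**

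- Expected 95% half-width for a risk difference: 1.96 × 0.1255 = 0.246 at 20 per arm; 1.96 × √(0.315 / 15) = 0.284 at 15 per arm.
- If 25% vs 15% is true, the drug arm's observed rate equals or exceeds that of linkage-alone with probability 0.27 at 20 per arm and 0.32 at 15 per arm.

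**The case against.** The strongest reply is that the plan disarms its own number. The preceding sentence says power may be inadequate, and the figure is introduced as crude. Section IV.E lists the small sample as a limitation, makes feasibility the main aim and leaves effectiveness to a later trial. No passage derives the 45 to 60 range from the 80%, and no stopping rule or go/no-go criterion uses it. A reader who takes a null result as evidence against a drug would have to overlook those warnings.

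This stands as a limit on impact: the case for running the pilot does not rest on the figure. It does not rescue the figure. Calling an estimate crude suggests imprecision, whereas 80% is a conventional planning target that no reading above reaches. The following sentence, on reducing the number of participants required, also treats about 60 as a real requirement for this effect.

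The size of the overstatement does depend on the assumed test. At two-sided 5% it is nearly sevenfold (0.80 / 0.12 = 6.7). At one-sided 5%, which the directional hypothesis might support, it is about fourfold (0.80 / 0.197 = 4.1). The statement that a larger effect raises power is true and is not in dispute.

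**Conclusion.** The concern holds. For the rates and sample size that section IV.F itself gives, power is about 12% (7% by Fisher) at 20 per arm and about 10% (4% by Fisher) at 15 per arm, against about 80% stated. The exact percentages rest on 1:1:1 allocation and a two-sided 5% test, which the plan does not specify. The conclusion that power is far below 80% does not rest on them, since it survives every allocation of the 60 and every relaxed alpha tried. It must be fixed: this is the protocol's only power figure, it concerns the primary clinical outcome, and it is false on its own inputs.

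**What to change.** In section IV.F, delete the 80% statement or replace it with wording such as: *Assuming 20 per arm and a two-sided 5% test, power to detect 25% vs 15% is about 12% (about 7% by Fisher's exact test); 80% power would need about 250 per arm.*

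Then report re-admission as estimation, as Aim 2's own wording already implies: each arm's rate and each drug-minus-linkage risk difference, with 95% confidence intervals. State the expected half-width in advance, about 25 percentage points at 20 per arm and about 28 at 15, so that readers can set it against the assumed 10-point effect.

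The cost is wording and reporting only. No extra patients are needed and neither design nor conduct changes; one stated figure becomes less favourable.

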### IV. Research Methods

#### A. Outcome Measure(s):

See table 1 for primary and secondary outcomes. In brief, our primary outcomes will be those related to feasibility as well as risk of 30-day all-cause hospital re-admissions. Secondary outcomes include risk of 30-day all-cause emergency department visit,

differences in readiness-to-change, and likelihood of having an alcohol metabolite (EtG) in the urine at follow-up.

*Table 1 Primary and secondary outcomes*

	Study Aim	Description	Instrument(s)
1' feasibility outcomes	1	Recruitment rate (# enrolled / month), follow-up rate, patient acceptability, adverse effects	Chart review, questionnaires
1' clinical outcome	2	Risk of 30-day all-cause hospital re-admissions	Chart review
2' clinical outcomes	2	Risk of 30-day all-cause ED visits	Chart review
	2	Within-subject difference in readiness-to-change 	Questionnaire
	2	Laboratory(+) for alcohol at SUDS	Urine EtG
	2	Percent of binge drinking days  since discharge	Questionnaire

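### Readiness-to-change has neither by-arm reporting nor a drug-versus-linkage contrast, and Section C gives two conflicting orders for baseline data and randomization (minor)

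*Combined protocol and SAP*

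**What the plan says.** **Analysis.** Table 1 (Section IV.A) assigns five outcomes to Aim 2. Section F, Data Analysis Plan, treats them as follows.

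- 30-day re-admission: "Rates of the two medication intervention groups (XR naltrexone or IV ketamine) will be compared against the group" that had linkage alone.
- 30-day ED visits: "This will be evaluated in a similar manner as hospital re-admissions".
- Binge drinking: "the proportion of binge drinking days since discharge will be calculated for each group".
- Urine EtG: "Proportions of positive urine ethyl glucuronide (EtG) will also be tabulated for each group".
- Readiness-to-change, defined in Table 1 as "Within-subject difference in readiness-to-change": "For those who follow-up, a mean of pre/post differences will be calculated, and a paired t-test will be used", with a null hypothesis of zero difference. No group is named, and the plan does not say whether the test is pooled or run in each arm.

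**Order of steps.** The Section C narrative runs screening, consent, baseline data from the counselor team (ToD), then randomization. Table 4, in the same section, has one row for screening, consent and randomization, where the assigned group is recorded. An arrow leads from it to a later row for baseline data, which includes SOCRATES-8A, PHQ-9 and the drinking history (TLFB). The trial is open-label.

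**The concern.** Aim 2 is organised by randomized group, and the pilot is meant to supply estimates for a larger trial. A test of change from zero does not compare groups. A significant result could reflect linkage, recovery after hospitalization, regression to the mean, or a delayed effect of the consult, all of which can act in every arm. A reader of the results would learn whether attenders changed, but not whether either drug added anything to linkage.

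The order of steps bears on the same outcome, because the baseline SOCRATES-8A is the pre score. If it is completed after the patient knows the assignment, part of any difference between arms could be a reaction to the assignment. Staff following Table 4 would also work differently from staff following the narrative.

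**Working it through.** **1. Coverage of the Aim 2 outcomes in Section F**

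| Outcome | By-arm reporting | Contrast with linkage-alone |
|---|---|---|
| Re-admission | yes | yes |
| ED visits | yes (same manner) | yes (same manner) |
| Binge drinking days | yes | none stated |
| Urine EtG | yes | none stated |
| Readiness-to-change | none stated | none stated |

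Readiness-to-change is the only one with neither.

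**2. What the paired test responds to**

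The documents give no expected change, so this is an illustration. Assume every arm changes by the same d (in SDs of the change score), there is no drug effect, the test is pooled, and alpha is 0.05 two-sided (the plan states none). With n attenders, the rejection probability is

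P(|T| > t(0.975, n−1)), where T is noncentral t with n−1 df and noncentrality d√n.

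For d = 0.5:

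- n = 5: critical value 2.776, noncentrality 0.5 × √5 = 1.118, probability 0.141.
- n = 30: 2.045, 2.739, probability 0.754.
- n = 45: 2.015, 3.354, probability 0.907.

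Range over the assumed d:

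| Attenders | d = 0.3 | d = 0.5 | d = 0.8 |
|---|---|---|---|
| 5 | 0.08 | 0.14 | 0.28 |
| 30 | 0.36 | 0.75 | 0.99 |
| 45 | 0.50 | 0.91 | >0.99 |

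All of these rejections occur with no drug effect. If the test were run within each arm, the same formula would apply with that arm's n, and the null hypothesis would still be zero change.

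**3. How precise a between-arm estimate could be**

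For an ANCOVA of the SUDS-visit score on arm and baseline, with m attenders in each of three arms and pre/post correlation r (assumed 0.3 to 0.7), the 95% CI half-width for a drug-minus-linkage difference, ignoring chance baseline imbalance, is

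t(0.975, 3m−4) × √(2/m) × √(1−r²), in SDs of the SUDS-visit score (not the change-score SD of step 2).

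- m = 15: 2.020 × 0.365 × √(1−r²) = 0.70, 0.64 and 0.53 for r = 0.3, 0.5 and 0.7.
- m = 5: 2.201 × 0.632 × √(1−r²) = 1.33, 1.21 and 0.99.

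**4. How many may attend**

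Section III reports that 2 of 17 referred patients presented within a month, before any enhanced linkage or payment: 2/17 = 11.8%. At that rate, 45 × 0.118 = 5.3 and 60 × 0.118 = 7.1, so about 5 to 7 attenders across all three arms. Linkage and payment are intended to raise this.

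**5. The two orders side by side**

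- Narrative: consent → baseline data → randomization.
- Table 4: consent and randomization, assigned group recorded → baseline data.

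Table 4's remark that the counselors collect baseline data first does not settle it, because it orders those data against the biopsychosocial intake. Both orders place baseline before the intervention. The text available for review does not say when the patient learns the assignment; consent pages are not part of it.

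**The case against.** The strongest defence is that the pre/post test is deliberate. Table 1 calls the outcome a within-subject difference, the plan claims no drug attribution for it, and Section F introduces the secondary utilization outcome as descriptive. That stands. But a within-subject change can be reported by arm just as binge drinking and EtG are. Consistency with those two would require only by-arm means; the ANCOVA contrast goes a step further and is justified as an exploratory estimate for planning.

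Several stronger readings are tempting and are not supported.

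- *Readiness is the only outcome without a drug-versus-linkage comparison.* It is not: binge days and EtG have no stated between-arm test either.
- *Motivational interviewing and payment given to all arms drive the change.* The consultation that "includes behavioral components such as supportive therapy and motivational interviewing" takes place before consent and baseline, so only a delayed effect could enter the change. The $20 is paid on completing follow-up data, after the post score, so only its anticipation could act.
- *Separate within-arm p-values will be set side by side and read as a drug effect.* The plan proposes no such comparison.
- *Assignment-aware answers corrupt the baseline tests that* "will help evaluate the effectiveness of randomization". Those tests cover demographic and baseline clinical data, and Table 4 lists such data separately from SOCRATES-8A, PHQ-9 and TLFB. Whether the scales are included is unclear.
- *The post score is undefined because SOCRATES-8A is also taken at 40 minutes.* That score exists only in the drug arms, and the restriction to patients who follow up points fairly clearly to the SUDS visit. A clarifying phrase is enough.

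There is also a practical objection. The consult service randomizes, a different team collects baseline data, and discharge is not always predictable. This is a real cost of the reordering.

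**Conclusion.** Both points hold as minor improvements. Section F gives readiness-to-change no by-arm estimate and no contrast with linkage-alone, and its planned test cannot inform drug versus linkage. The absence is plain from the text. The 14%, 75% and 91% illustrate the consequence and rest on an assumed shared change of 0.5 SD, a pooled test and two-sided 0.05; the documents do not predict such a change.

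The narrative and Table 4 contradict each other on whether baseline data precede randomization. Following Table 4 would allow the pre score, PHQ-9 and TLFB to be answered with the assignment known. The documents give no basis for a size, and none is claimed. No primary outcome is affected: recruitment, follow-up, acceptability, adverse effects and re-admission do not depend on either point.

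**What to change.** 1. In Section F, report mean SOCRATES-8A change from baseline to the SUDS visit by arm, naming that visit as the post time point. Add each drug-minus-linkage difference with 95% CI from an ANCOVA of the SUDS-visit score on arm and baseline.
2. Show SUDS attendance by arm beside it. Label the estimate exploratory, imprecise and limited to attenders, with possible bias if attendance depends on readiness after treatment. If attenders are very few, tabulate by arm only. At the historical attendance rate that would be the likely outcome.
3. Reconcile the narrative and Table 4 by reordering Table 4 to match the narrative: consent, baseline forms, then randomization and release of the assignment.

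The cost is two or three sentences in Section F and a reordering of Table 4, with no new data. The downside is that assignment must wait until the ToD team has finished the baseline forms, which needs a handoff back to the consult service before a discharge whose date may be uncertain.

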### ***Data Collection***

Data will be primarily collected at four time-points (Table 4). Data will be entered by staff into a REDCap database on tablet computers in the hospital and at SUDS clinic. Data collected at enrollment will primarily be descriptive, including demographics, recent drinking history, readiness to change, and various contributing factors to drinking. Immediately after intervention, vital signs,

symptoms, and acceptability will be recorded. Data collected on post-discharge arrival to SUDS clinic will include most 2' clinical outcomes. We will obtain re-admission rate (1' clinical outcome) through chart review, conducted by research team members at 30-days post-discharge.

Table 4 Patient flow and data collection points

Step	Who	Notes	Data collected – staff entered
Patient identified on consult list	ACS	Quick screen that meets inclusion criteria	
↓			
Addiction consult performed	ACS	Evaluation, withdrawal management, medication (though if patient consents to study, will not be prescribed an addiction medication at discharge), brief therapy, referrals, disease screening/harm reduction	
↓			
Screen, consent, randomization	ACS	Formal screen to identify any exclusion criteria. Simple randomization by algorithm	
 
• E-Consent (should include consent to see records in “care everywhere” – some hospitals require permission – when checking for ED visits and re-admissions)
 
• Screening documentation (inclusion and exclusion criteria)
 
• Alcohol-related admissions in last 12 months (date, location, top 3 diagnoses)
 
• Assigned group
 

↓			
Baseline data, referral to SUDS [data collection point #1]	ToD	ToD collects baseline data first, then performs “biopsychosocial intake” and sets up SUDS appointment within 1 week of discharge.  Discharge date is not always predictable;	
 
• Demographics
 
• Baseline clinical data
 
• Depression symptoms baseline (PHQ9 2 wks)
 
• Drinking History 7-days prior to admission (TLFB)
 
• Readiness to change (SOCRATES-8A)
 
• ACE Questionnaire
 

		ACS to review active hospitalized research participants and contact ToD/update date in RedCap as needed.	
↓			

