Intervention administered [data collection point #2]	RN, ACS	
For 'linkage-alone' group, data to be entered following consult.
 
For NTX group, intervention administered prior to discharge (could be same day as consent). Vitals immediately preceding and 40 min post- injection. Data collected after administration.
 
For KET group, intervention administered prior to discharge (could be same day as consent), though should have no food for at least 3 hours (~50% gastric emptying). Vitals immediately preceding, after completion, and 2 hours following end of intervention.
	
 
Vital signs (HR, BP, O2): linkage-alone group- baseline only, recorded after consult. NTX group- baseline, 40 min after administration. KET group- baseline, end of administration (~40min), 2 hours after end of administration.
 
Most recent AST, ALT
 
UDS-5 data
 
[for KET] Dissociative symptoms (CADSS) after administration (40 min)
 
[for NTX and KET] Acceptability of intervention (10-point Likert) after administration
 
[for NTX and KET] Readiness to change (SOCRATES-8A) after administration (40 min)
 
 
ORDER: CMP (if not already obtained), UDS-5 (if not already obtained)
 
ORDER in discharge orders (outpatient): CMP, UDS-5, urine EtG (if not already ordered)

↓			
Presentation to SUDS, data entered, contingency management reward administered [data collection point #3]	SUDS staff	
Upon presentation, staff to collect study data. After completion, will receive contingency management reward.
 
Then patient to complete standard intake/follow-up visit, if willing.
	
 
Drinking History since discharge (TLFB since discharge)
 
Depression symptoms (PHQ9 modified to read "since discharge.")
 
Readiness to change (SOCRATES-8A)
 
[for KET] Dissociative symptoms (CADSS)
 
Adverse Events (Modified PRISE)
 
Acceptability of intervention (10-point Likert)
 

		Staff to instruct patient to present to the clinic laboratory (e.g. pav G) for CMP after the visit.	
 
Contingency management feedback (10-point Likert, open ended)
 

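### Percent of binge drinking days is reported as a raw group proportion, although each patient's own pre-admission value is collected and could reduce random error in the group comparison

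*Combined protocol and SAP*

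**What the plan says.** - **Outcome.** Table 1 (IV.A) lists "Percent of binge drinking days" since discharge as a secondary clinical outcome under Aim 2.
- **Baseline measure.** Table 4 (IV.C), data collection point 1, includes "Drinking History 7-days prior to admission (TLFB").
- **Follow-up measure.** Data collection point 3, on presentation at the SUDS clinic, includes "Drinking History since discharge (TLFB since discharge"). On timing, "Patients will be assigned a follow-up within 7 days of discharge".
- **Analysis.** IV.F says "the proportion of binge drinking days since discharge will be calculated for each group". It names no baseline term, change score, group difference, test or interval for this outcome.
- **Role of baseline data.** IV.C states that "Data collected at enrollment will primarily be descriptive". IV.F compares baseline data between groups to check the randomization, but does not say what follows if they differ.
- **Design.** The trial is an "open-label, pilot feasibility trial (n=45-60"), and "Patients will undergo a simple randomization algorithm to one of three arms". Stratification and blocking are not mentioned.
- **Another outcome treated differently.** For readiness-to-change, IV.F uses each patient's difference between baseline and follow-up.

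**The concern.** The outcome and its own baseline are recorded with the same instrument, yet the baseline is left out of the analysis. Simple randomization of 45-60 patients into three arms leaves balance on prior drinking to chance. If pre-admission binge drinking predicts binge drinking after discharge, part of the scatter in the three group proportions only reflects who was allocated where. That part can be removed with data already in hand.

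What is at stake is the precision of an exploratory Aim 2 estimate. The current wording also leaves open whether days are pooled within a group or averaged over patients, so the quantity to be reported is not fully defined.

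**Working it through.** The plan gives no figure for this outcome to reproduce. Its only power statement concerns re-admission and is not used here.

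**Inputs from the documents.** N = 45-60 (IV.C), so 15-20 per arm if the arms come out equal and everyone attends. Historical clinic attendance is 11.8%, or 2 of 17 (II and III), before enhanced linkage.

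**Assumed inputs.** The correlation r between baseline and follow-up percent binge days (0.3, 0.5, 0.7); the SDs (30-40 points, the same at both times); and attendance above the historical rate.

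**Step 1: chance imbalance.** With m measured patients per arm, the baseline difference between two arms has standard error √(2/m) in baseline SDs.
- m = 20: √(2/20) = 0.32
- m = 15: √(2/15) = 0.37
- m = 7.5 (half of 45 attend): √(2/7.5) = 0.52

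**Step 2: effect of adjustment.** In a three-arm linear model with one baseline covariate and N patients measured, the variance of an arm difference relative to the raw one is (1 − r²) × (1 + 1/(N − 5)). The second factor is the price of estimating the slope.

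| N measured | r = 0.3 | r = 0.5 | r = 0.7 |
|---|---|---|---|
| 60 | 0.91 × 1.018 = 0.93 | 0.75 × 1.018 = 0.76 | 0.51 × 1.018 = 0.52 |
| 45 | 0.91 × 1.025 = 0.93 | 0.75 × 1.025 = 0.77 | 0.51 × 1.025 = 0.52 |
| 22 | 0.91 × 1.059 = 0.96 | 0.75 × 1.059 = 0.79 | 0.51 × 1.059 = 0.54 |

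At N = 60 the reductions are about 7%, 24% and 48%.

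**Step 3: break-even.** Setting the ratio to 1 gives r = √(1/(N − 4)).
- N = 60: √(1/56) = 0.13
- N = 45: √(1/41) = 0.16
- N = 22: √(1/18) = 0.24
- N = 7: √(1/3) = 0.58

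At 11.8% attendance, 0.118 × 45 = 5.3 and 0.118 × 60 = 7.1, so about 5-7 patients in all three arms together would have the outcome.

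**Step 4: in percentage points.** The raw standard error is SD × √(2/m).
- SD 30, m = 20, r = 0.3: 30 × √(2/20) = 9.5 raw. Adjusted, 9.5 × √0.93 ≈ 9.1. The gain is about 0.4 points.
- SD 40, m = 10 (N = 30), r = 0.5: 40 × √(2/10) = 17.9 raw. Adjusted, the ratio is 0.75 × (1 + 1/25) = 0.78 and 17.9 × √0.78 ≈ 15.8. The gain is about 2.1 points.

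**Step 5: simulation with 7-day windows.** Two arms were simulated, each patient having seven baseline and seven follow-up days. The mean binge proportion was 0.67 or 0.86 at baseline and about 0.37 at follow-up (assumed). The observed r was 0.16-0.42. The adjusted-to-raw variance ratio was 0.85-1.01 at 15-20 per arm and 0.88-1.07 at 8 per arm. So short windows and a high baseline give anything from a modest gain to a small loss.

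**The case against.** The strongest reply is that the plan makes no formal comparison on this outcome. It tabulates a proportion per group in a trial whose main aim is feasibility, and the sentence in IV.F about parameter estimates closes the paragraph on re-admission. Adding a model and intervals therefore goes beyond what was planned. This limits the consequence but does not remove the point. Three proportions of an Aim 2 outcome, shown side by side, will be compared. The plan also already uses a patient's own baseline for readiness-to-change, although only to test change from zero and not to compare arms.

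The remaining objections bear on size, and they stand:
- No correlation or SD is given, and the gain may be nil.
- Having 10-20 measured per arm needs 50-100% attendance at N = 60, against a documented 11.8%.
- The follow-up covers few and unequal numbers of days, and the outcome is bounded, so a linear model with small arms gives only approximate intervals.

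Three stronger readings are tempting but unsupported:
- **That omitting the baseline biases the result.** Chance imbalance after randomization is random error already inside the raw standard error. Carry-over of r × √(2/m), about 0.09, 0.16 and 0.22 outcome SDs at 20 per arm for r = 0.3, 0.5 and 0.7, is the same component as the variance reduction and must not be counted as an extra error.
- **That 1 − r² = 0.51 at r = 0.7 is the saving.** It is the variance remaining. The cut is 49%, or about 48% after the cost of the covariate.
- **That adjustment would make the comparison representative of all randomized patients.** It does not remove selection by clinic attendance.

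**Conclusion.** The point holds as a minor, low-cost improvement. The baseline of this outcome is collected and unused, and under simple randomization with at most about 15-20 measured patients per arm that leaves avoidable random error in the group comparison.

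The saving in variance is about 7%, 24% or 48% at N = 60 for an assumed r of 0.3, 0.5 or 0.7. The simulation with 7-day windows, where r did not exceed 0.42, suggests the lower part of that range. Adjustment gains nothing if r is below about 0.13 (N = 60) to 0.24 (N = 22). A baseline near its ceiling would push r towards that region. At historical attendance, adjustment would not be worth fitting. No primary outcome and no planned test is affected.

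**What to change.** In IV.F:
1. Define percent binge days per patient, as binge days divided by days covered since discharge, and state that group figures average these.
2. Report each drug-minus-linkage difference with a 95% CI from a linear model with arm and baseline TLFB percent binge days, beside the unadjusted figures.
3. If too few patients attend to fit the model, give unadjusted descriptive figures only. State that minimum in advance.
4. Label the result exploratory and limited to clinic attenders.

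In IV.C, reconcile the order of events. The narrative has baseline data obtained before randomization, while Table 4 lists baseline data after it. The covariate should be taken before assignment is known.

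The cost is a few sentences and one model, with no new data or visits. The downside is one degree of freedom and a possibly negligible gain. Specifying the adjustment now also avoids choosing it after an imbalance has been seen.
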